9.2 Secondary Efficacy Assessments

9.2.1 Absolute PSA Response

Failure to achieve a PSA of $\leq 4\text{ ng/ml}$ after seven months of combined ADT has been shown to be a negative predictor for survival in the SWOG 9346 trial.(63) We will report the PSA nadir value after initiation of study drugs and measure the absolute and relative PSA declines from the baseline PSA at the time of study enrollment.

9.2.2 Time to PSA Nadir

We will assess the time to PSA nadir, which is defined as the time to achieve the lowest PSA value after initiation of study drugs. The prognostic significance of the time to PSA nadir is yet to be defined but Choueiri et al. suggested that a faster time to reach a PSA nadir after the initiation of ADT was associated with shorter survival duration in men with hormonal naïve metastatic prostate cancer.(64)

9.2.3 Safety and Toxicity

We will assess the safety and toxicity of this drug combination through routine history and physicals as well as serial monitoring of blood work, all of which will be recorded and reviewed periodically. Adverse events will be defined according to CTCAE version 4.0 (Appendix C).

9.3 Tertiary (Exploratory) Efficacy assessments

9.3.1 Change in Bone Health

ADT is known to effect bone strength. Compared to men with prostate cancer who do not receive treatment with ADT, patients with prostate cancer treated with ADT have a 13-30% increased risk of osteoporotic fractures.(65) Loss of lean muscle mass coupled with declined strength from ADT predisposes to a high risk of falls, which in the setting of osteoporosis leads to increased fracture risk. To determine the impact of study treatments of bone health, we will assess changes in bone density by comparing results of DEXA scans prior to and at the end of study treatment. To accurately examine their impact on bone health, only patients who are on the study drugs for at least 1 year will be included for this analysis. Additionally, due to the bone strengthening effects of bisphosphonates and denosumab, patients who receive these therapies will be excluded from this secondary endpoint analysis.

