7.2.1 Prohibited Medications

The following medications are prohibited within 4 weeks prior to the start of study drug treatment and are prohibited during the course of the study:

- Chemotherapeutic, immunotherapeutic and biologic agents
- Systemic glucocorticoids greater than the equivalent of 10 mg per day of prednisone/prednisolone (unless needed for stress steroids or to treat presumed adrenal insufficiency)
- Estrogens
- Herbal medications that may affect PSA levels (i.e., saw palmetto)
- Androgens (testosterone, dihydroepiandrosterone [DHEA], etc.).

Use of bisphosphates or rank-ligand inhibitor is allowed but doses should be documented during the study period.

The use of strong or moderate CYP2C8 or CYP3A4 inducers or inhibitors (see Appendix F) is prohibited while on study for patients receiving dutasteride.

Patients on therapies known to be weak inhibitors/inducers or narrow-therapeutic-index substrates of CYP2C8 or CYP3A4 should be evaluated for clinically significant drug interactions, but may participate in the study with appropriate monitoring and management.

Deviation from the above guidelines should occur only if absolutely necessary for the well-being of the patient. Any deviations to the medication/treatment guidelines are to be recorded.

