¤ After disease progression, follow-up will occur every 6 months (+/- 2 months) for first year after disease progression and as clinically indicated thereafter. Each subsequent antineoplastic therapy and survival status are the only required data point following progression.

¤ Comprehensive geriatric assessment (CGA) will be performed at baseline, end of cycle 1 and every 24 weeks during the study protocol until week 61 and at the time of progression. FACT-P will be performed along with CGA

¤ DEXA scan must be obtained within 2 years prior to registration for all patients. Follow-up DEXA scans should be obtained after 2 years of protocol treatment for patients not receiving denosumab or bisphosphonates. DEXA scan is not indicated for those who are on treatment with bisphosphonates or denosumab.

¤ For patients without radiographic evidence of metastatic disease at enrollment of study protocol, disease assessment with radiographic studies are not necessary unless there is evidence of PSA progression (see Section 6.0) or clinically indicated. For patients with radiographic evidence of metastatic disease at enrollment of study protocol, disease assessment with radiographic studies should be performed as indicated in the above study calendar and may be performed more frequently if clinically indicated by the same methods used at baseline. Chest Imaging may include either chest X-ray or CT chest at the discretion of the treating physician. After week 97, for patients with stable PSA, scans to be performed at the time of progression or as clinically indicated

¤ Treatment will be given daily and will continue until disease progression or other reason for discontinuation of protocol treatment (see Section 7.4) Study drug will be dispensed every 12 +/- 4 weeks and a 120 day supply of medication will be provided at each visit.

¶ This procedure is not mandatory but should be discussed with all patients enrolled in the protocol and can also be considered during the treatment course to prevent further worsening of breast tenderness when considered appropriate..

¤ Followed until death, study closure, or withdrawal of consent.

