10.3 Tertiary Endpoints

10.3.1 Changes in BoneHealth

This will be expressed as a difference between the mean T scores on bone densitometry at baseline and at 2 years of follow-up (Section 8.0). A 95% confidence interval for the difference will be constructed using the standard approach for paired measurements [67]. We will also compute the frequency and the percentage of subjects with osteopenia (T score = -1.0 to -2.5) and osteoporosis (T score < - 2.5) at baseline and at 2 years of follow-up.

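### The bone-density analysis excludes men who start a bisphosphonate or denosumab on study along with those on one at Day 1, which can make the DEXA result look too favourable by an unknown amount

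*Combined protocol and SAP*

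**What the plan says.** Section 2.3 makes bone health an exploratory objective. Section 9.3.1 describes the assessment: "we will assess changes in bone density by comparing results of DEXA scans prior to and at the end of study treatment". It sets a minimum exposure, "only patients who are on the study drugs for at least 1 year will be included for this analysis", and then the exclusion: "due to the bone strengthening effects of bisphosphonates and denosumab, patients who receive these therapies will be excluded from this secondary endpoint analysis". The sentence calls the endpoint secondary, although the section heading and Section 2.3 make it tertiary.

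Section 7.2.1 permits these agents on study: "Use of bisphosphates or rank-ligand inhibitor is allowed but doses should be documented during the study period". The Section 8.0 footnotes tie the follow-up scan to current use: "Follow-up DEXA scans should be obtained after 2 years of protocol treatment for patients not receiving denosumab or bisphosphonates", and "DEXA scan is not indicated for those who are on treatment with bisphosphonates or denosumab". A baseline DEXA within 2 years before registration is required for all men.

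Section 10.3.1 plans two summaries. One is the "difference between the mean T scores on bone densitometry at baseline and at 2 years of follow-up", with a paired 95% interval. The other is "the frequency and the percentage of subjects with osteopenia" and with osteoporosis, at baseline and at 2 years. It plans no count of excluded men, no reason for starting an agent and no sensitivity analysis.

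**The concern.** Excluding men already on a bone agent at Day 1 is a baseline restriction. It narrows the population but does not distort the change within it. Excluding men because they later start an agent conditions on a post-baseline event that bone loss or a fracture can cause. If some starts happen for that reason, the men who remain have lost less bone than the men who entered, and there is no control arm to reveal the shift.

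The clearest case is a start after the 2-year scan. Treatment and follow-up continue beyond week 97 in Section 8.0. A man whose 2-year DEXA shows loss, and who is then given an agent, has two scans untouched by that agent. The stated reason for exclusion, that these drugs strengthen bone, cannot apply to them. Yet Section 9.3.1 has no time limit and would remove the pair because of what it showed.

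At stake is the one planned bone-density result, in a trial whose background (Sections 1.0 and 9.3.1) cites osteoporosis and fracture among the harms of ADT.

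**Working it through.** The documents give no planning figure for the bone endpoint, so there is nothing to reproduce. The check covers how the passages fit together, the direction of bias, and how many men contribute.

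**1. The passages side by side.** Section 9.3.1 excludes on receipt, at any time and for any reason. Section 8.0 withholds the follow-up scan on current use. A start before 2 years therefore usually leaves no follow-up scan. A start after 2 years leaves a valid scan, which 9.3.1 drops. The only scheduled on-study DEXA comes after 2 years of treatment, so an earlier start prompted by on-study loss needs a fracture or an off-schedule scan.

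**2. Direction and size of bias in mean T-score change.** Let a share q of men be excluded, those lowest on a score that correlates ρ with T-score change. For normal variables, the mean in those kept is too high by

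bias = ρ × SD × φ(z_q) / (1 − q).

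None of the inputs is in the documents. Assumed: q = 10% to 30%, mean change −0.30, SD of change 0.40, baseline T score with mean −1.5 and SD 1.0. At q = 0.20, φ(z_q)/(1 − q) = 0.280/0.80 = 0.350, so:

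- Starts follow the largest losses (ρ = 1): 1 × 0.40 × 0.350 = 0.14.
- Starts follow loss plus equal noise (ρ = 1/√2 = 0.71): 0.71 × 0.40 × 0.350 = 0.10.
- Starts follow low current T score (ρ = 0.40/√(1.0² + 0.40²) = 0.37): 0.37 × 0.40 × 0.350 = 0.05.
- Starts follow baseline T score only, or are unrelated to bone (ρ = 0): 0.

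A simulation of 400,000 men with the same inputs agrees. It also gives the shift in the 2-year osteoporosis percentage (T score below −2.5), kept men minus all men:

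| Starts driven by | Mean-change bias at q = 10% / 20% / 30% | Osteoporosis shift, points |
|---|---|---|
| Largest on-study loss | +0.08 / +0.14 / +0.20 | −2.7 / −4.7 / −6.5 |
| On-study loss plus noise | +0.06 / +0.10 / +0.14 | −1.8 / −3.2 / −4.5 |
| Low current T score | +0.03 / +0.05 / +0.08 | −8.2 / −18.6 / −25.8 |
| Baseline T score only | 0.00 / 0.00 / 0.00 | −8.0 / −15.7 / −21.1 |
| Nothing related to bone | 0.00 / 0.00 / 0.00 | 0.0 / 0.0 / +0.1 |

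With two other assumed distributions of change (mean −0.2, SD 0.3; mean −0.5, SD 0.5) included, the mean-change bias runs from +0.02 to +0.25 whenever starts depend on on-study loss. No mechanism tried moved it the other way. All figures refer to the change a man would have had without the agent.

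The baseline-only row needs care. Men excluded for low baseline density leave the baseline percentage as well as the 2-year one, so that shift says who was studied more than what the drugs did.

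**3. How many men contribute.** The follow-up scan requires 2 years of protocol treatment, and treatment stops at progression. Section 10.1 uses 0.40 for 2-year PSA-PFS in its margin-of-error formula: 40 × 0.40 = 16 men. At its alternative median of 3.04 years, if times are exponential, 0.5^(2/3.04) = 0.634 and 40 × 0.634 = 25 men. Both counts come before any exclusion for bone agents.

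**4. What a few men do (assumed example).** Of 16 men scanned at 2 years, 4 have osteoporosis and 2 of those 4 then start an agent. All scans give 4/16 = 25%. The literal rule gives 2/14 = 14%.

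**The case against.** The strongest reply is that the calendar blocks most of the mechanism. Before 2 years no scheduled scan shows a physician that density has fallen. The reasons for starting that the documents make visible are low density on the pre-study DEXA and bone metastases, which are eligible under Section 5.2.1. Starts driven by baseline density give about zero bias in mean change, and starts for metastases need not bias it in this way. If a fracture counts as a skeletal-related event, Section 7.4 already ends treatment. This stands. It means the bias may be small and its lower bound is zero. It does not cover off-schedule scans, other fractures, or the start after the 2-year scan.

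A sensible analyst might also read the exclusion as applying only to agents received before the follow-up scan. That would be reasonable, but the text does not say it.

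A reader might infer that the rule hides the worst bone outcomes and flatters bone safety overall. The documents do not support that. Section 11.0 requires adverse events to be documented whether or not related to treatment. The safety text in Section 10.2 summarises them by type and grade and describes each grade 3 or 4 event. Section 6.0 lists skeletal-related events among the assessments, and the geriatric assessment records falls. None of these excludes bone-agent users. Nor do the documents support a claim that the bias is large, since no rate of starting or reason for starting is given.

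Finally, the endpoint is exploratory, with no test and no precision target. That limits the consequence, but the correction is correspondingly cheap.

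**Conclusion.** The point holds for the DEXA summary. The exclusion in Section 9.3.1 mixes a baseline restriction with a post-baseline one, and the second can be caused by the outcome. The resulting error, if any, is towards less apparent bone loss. Its size cannot be known from the documents: it is zero for mean change if no start depends on on-study loss, and it grows with the share of starts that do. The 0.02 to 0.25 T-unit range rests wholly on assumed start rates, SDs and start mechanisms. The upper part requires starts to track a loss that no scheduled scan measures before 2 years, so it should not be taken as an expectation. What is certain is that the literal wording can discard a valid scan pair, that the plan would not report how many men were excluded or why, and that with roughly 16 to 25 men at 2 years a few such exclusions could change the reported percentages.

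**What to change.** Change the wording in Sections 9.3.1 and 10.3.1; add no scans and leave the concomitant-treatment rules as they are.

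1. Exclude for prior use only men taking a bisphosphonate or denosumab at Day 1.
2. For men who start later, keep any follow-up DEXA done before the start, including a 2-year scan that precedes it.
3. Report the number of men starting an agent, with date and reason: bone metastasis, low baseline density, or on-study loss or fracture.
4. As a sensitivity analysis only, show the 2-year osteoporosis percentage with and without counting as unfavourable those starts made for documented on-study bone loss or fragility fracture. Do not count starts for low baseline density, which would bias the result the other way.

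While editing, align the follow-up time point: Section 9.3.1 refers to the end of treatment after at least 1 year, and Section 10.3.1 to 2 years.

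The cost is one extra field for the reason, since Section 7.2 already collects concomitant medications and Section 7.2.1 the doses. The limit is that a man who starts before any follow-up scan still contributes no T-score change; he is visible only in the count and, where the reason qualifies, in the sensitivity percentage.

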9.3.2 Change in CGA Domains

ADT, which includes orchiectomy or administration of GnRH agonists/antagonists, remains the mainstay of treatment for hormone naïve patients who present with biochemical recurrence or metastatic disease. Testosterone depletion secondary to ADT causes a myriad of side effects, which include decreased libido, muscle strength, increased risk of falls and cognitive changes. All these changes have been well characterized and captured using a CGA in numerous studies. The current trial would be utilizing periodic CGA to capture any side effects related to the study drug combination that would otherwise not be recognized to provide a better understanding of the safety profile of the drug combination specifically in the vulnerable/frail elderly population.

During geriatric assessments, the various domains as listed in the table below will be measured

DOMAIN	TOOL	SCORE SIGNIFYING IMPAIRMENT
Physical function	➤ ADL ➤ IADL ➤ Fall history	➤ Any ADL or IADL impairment ➤ Any history of fall

Objective physical performance	➤ SPPB	➤ ≤ 9
Comorbidity	➤ Average number of comorbid conditions	➤ > 5
Nutrition	➤ BMI ➤ MNA	➤ <21 ➤ ≤ 11
Social support	➤ OARS Medical Social Support	➤ Any deficit noted
Polypharmacy	➤ Number of total medications	➤ ≥ 5 medications
Psychological	➤ GDS	➤ ≥ 5
Cognition	➤ BOMC ➤ MoCA	➤ > 10 ➤ <26
Screening	➤ VES-13	➤ ≥ 3

ADL: Activity of daily living

MNA: Mini nutritional assessment

SPPB: Short physical performance battery

BMI: Body mass index

VES: Vulnerable elderly survey

GDS: Geriatric Depression scale

IADL: Instrumental activity of daily living

BOMC: Blessed orientation-memory-concentration

MoCA: Montreal cognitive assessment

In a study published by Bylow et al., fifty elderly men (>70 years) receiving ADT for systemic Pca(80% with biochemical recurrence), underwent CGA at baseline (while on ADT) and three months later. (10) Fall history in the study population was also recorded. All domains listed in the above table were assessed during these visits. Of the 50 men, 24% had impairment in ADLs, 42 % had impairment in IADLs, 56% had abnormal SPPB findings and 22 % reported falls at the time of first assessment. Among the forty patients who completed the follow up CGA at 3 months, 20% had worsening SPPB scores and falls were common, even in patients with no prior falls. The results of this study demonstrated that a substantial number of elder patients are vulnerable to frail at baseline, and are at risks of significant functional and physical decline after even short term ADT. This study also reiterates that CGA adds significant information in not only documenting baseline health status but is also instrumental in monitoring toxicities that would otherwise not be captured. More importantly, administration of serial CGA is feasible and hence, the current study will utilize serial CGA besides other tools to monitor adverse events

9.3.3 Quality of life assessments- Functional Assessment of Cancer Therapy - P

The FACT-P is a multidimensional, self-reported quality of life instrument specifically designed for use with prostate cancer patients. It consists of 27 core

items which assess patient function in four domains: Physical, Social/Family, Emotional, and Functional well-being, which is further supplemented by 12 site specific items to assess for prostate related symptoms. Each item is rated on a 0 to 4 Likert-type scale, and then combined to produce subscale scores for each domain, as well as a global quality of life score with higher scores representing better quality of life.

10.0 STATISTICAL CONSIDERATIONS

10.1 Primary End-Point

The primary efficacy end-point for this trial is PSA progression-free survival (PFS) defined as the length of time that a given subject will be alive and free from PSA progression. Median PSA-PFS and 1-year and 2-year PSA-PFS probabilities will be estimated using the Kaplan-Meier method, with 95% confidence intervals constructed based on Greenwood's variance estimator, which is the default approach in SAS 9.3. (66-68) Confidence intervals for the median are given by $\{t : \hat{S}(t) - 0.5\} \leq \chi^2_{\alpha/2} V[\hat{S}(t)]\}$, where t represents all time points satisfying the inequality, $\hat{S}(t)$ is the Kaplan-Meier

estimate of PSA-PFS, $\chi^2_{\alpha/2}$ is a chi-square score with one degree of freedom

corresponding to the chosen confidence level (for 95% confidence $\chi^2_{\alpha/2} = 3.84$), and

$V[\hat{S}(t)]$ is the Greenwood's variance estimator. [64] Confidence intervals for the 1-year and 2-year survival probabilities will be constructed as $\hat{S}(t) \pm z_{\alpha/2} V[\hat{S}(t)]^{1/2}$, where $z_{\alpha/2}$ is

the standard normal score. (67)

It should be noted that in the absence of loss to follow-up (i.e., if vital status and PSA-progression status are known for each subject at the end of the study), $\hat{S}(t)$ coincides

with the observed proportion of subjects alive and without PSA progression by time t and $V[\hat{S}(t)]$ coincides with the usual estimator of the variance of a sample proportion $V[\hat{S}(t)] = [\hat{S}(t)][1 - \hat{S}(t)]/n$, where n is the number of subjects in the study. [65]

Sample size justification: The median PSA-PFS times under null and alternatives hypothesis are assumed to be 1.44 and 3.04 years (the corresponding 1 year PSA-PFS rates are 50% and 72% respectively). Based on this assumption, the one sample log-rank test shows that a sample size of $n=36$ has 82% power (two-sided test with significance level 0.05) to reject the null hypothesis if the median survival time is at least 3.04 years. Taking into account of withdrawal or loss to follow-up (no more than 10% for the first year), we plan to recruit 40 patients in the study.

Expected margin of error (one-half of the confidence width) of the 95% confidence intervals for $S(t)$ can be approximated by $1.96 \sqrt{[\hat{S}(t)][1 - \hat{S}(t)]/n}$. For 1-year and 2-year PSA-PFS this gives $1.96 \sqrt{0.72 \times 0.28/40} = 0.15$, $\sqrt{0.40 \times 0.60/40}$

respectively. In addition to the number and percentage of subjects alive and without PSA progression at 1 and 2 years of follow-up, we will report separately numbers and percentages of subjects alive and with PSA progression, dead without PSA progression, and dead with PSA progression. The causes of death and the incidence of clinical progression will also be reported.

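### Untransformed Greenwood intervals for 1- and 2-year PSA-PFS cover about 92–94% at n=40 with loss to follow-up; log(-log) intervals come closer to 95% at almost the same width

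*Combined protocol and SAP*

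**What the plan says.** Section 10.1 makes PSA-PFS the primary endpoint. The median and the 1- and 2-year probabilities are to be estimated by Kaplan-Meier, "with 95% confidence intervals constructed based on Greenwood's variance estimator, which is the default approach in SAS 9.3". The landmark formula follows: "Confidence intervals for the 1-year and 2-year survival probabilities will be constructed as" the estimate plus or minus a standard normal score times the square root of Greenwood's variance. No transformation is named, and no truncation at 0 or 1. The median has its own interval, obtained by inverting an untransformed chi-square statistic.

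The planning figures are in the same section:

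- **Medians:** "The median PSA-PFS times under null and alternatives hypothesis are assumed to be 1.44 and 3.04 years".
- **1-year rates:** "the corresponding 1 year PSA-PFS rates are 50% and 72% respectively".
- **Sample size:** a one-sample log-rank test at n=36 that "has 82% power (two-sided test with significance level 0.05) to reject the null hypothesis if the median survival time is at least 3.04 years", raised for "withdrawal or loss to follow-up (no more than 10% for the first year"), so that "we plan to recruit 40 patients in the study".
- **Precision:** a margin-of-error calculation at n=40 with rates of 0.72 (1 year) and 0.40 (2 years).

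No rule compares the 1- or 2-year interval with a null value.

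**The concern.** An interval that is symmetric on the probability scale relies on the Kaplan-Meier estimate being close to normal with a well-estimated standard error. With 40 men and rates away from one half, the estimate is skewed. Its standard error also shrinks as the estimate rises, so a trial that happens to look good reports a short interval placed too high.

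This is a single-arm trial, so readers will judge the regimen largely by the estimate and its lower limit. A lower limit that is too high too often makes the result look more secure than it is. A transform that corrects most of this costs one sentence.

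**Working it through.** **Inputs from Section 10.1.** n=40; 95% level; 1-year rates 0.50 and 0.72; 2-year rate 0.40; medians 1.44 and 3.04 years; loss of at most 10% in year 1.

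**Assumptions added here.** Exponential event and loss times; loss of 10% per year, with 0% and 20% as the range.

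**Rates examined.** The stated medians and 1-year rates do not agree under an exponential model, so both readings were used.

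- From the medians: 0.5^(1/1.44) = 0.618 and 0.5^(1/3.04) = 0.796 at 1 year; squared, 0.382 and 0.634 at 2 years.
- From the 1-year rates: 0.50² = 0.25 and 0.72² = 0.518 at 2 years.
- The plan's own 2-year 0.40.

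**The plan's own precision figure.** Margin = 1.96 × √(S(1−S)/n).

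- 1 year: 1.96 × √(0.72 × 0.28/40) = 0.139.
- 2 years: 1.96 × √(0.40 × 0.60/40) = 0.152.

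The printed 0.15 matches the 2-year term. The equation is broken in the extracted text, so nothing is made of its position beside the 1-year term.

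**The two intervals.**

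- Linear: S ± 1.96 × SE.
- Log(-log): S^exp(±θ), with θ = 1.96 × SE / (S × |ln S|).

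Example with 29 of 40 event-free and no loss: S = 0.725 and SE = √(0.725 × 0.275/40) = 0.0706.

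- Linear: 0.587 to 0.863.
- Log(-log): θ = 1.96 × 0.0706/(0.725 × 0.3216) = 0.594, giving 0.559 to 0.837.

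With 16 of 40 the two nearly coincide: 0.248 to 0.552 and 0.250 to 0.546.

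**Coverage with 10% loss per year** (n=40; 40,000 simulated trials per row; Monte Carlo error about ±0.25 points):

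| True rate | Linear | Log(-log) | Mean width, linear / log(-log) |
|---|---|---|---|
| 1-year 0.50 | 93.7% | 94.9% | 0.315 / 0.309 |
| 1-year 0.618 | 93.8% | 95.2% | 0.306 / 0.303 |
| 1-year 0.72 | 92.9% | 95.6% | 0.282 / 0.284 |
| 1-year 0.796 | 92.0% | 95.5% | 0.251 / 0.260 |
| 2-year 0.25 | 92.8% | 95.0% | 0.281 / 0.272 |
| 2-year 0.382 | 93.4% | 94.9% | 0.316 / 0.307 |
| 2-year 0.40 | 93.6% | 95.0% | 0.318 / 0.309 |
| 2-year 0.518 | 93.8% | 95.3% | 0.324 / 0.318 |
| 2-year 0.634 | 93.5% | 95.3% | 0.312 / 0.309 |

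With 20% loss per year, at every rate above except 0.40, linear coverage is 92.4–93.9% and log(-log) coverage 95.0–95.8%.

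**Direction of the misses, 10% loss.** The nominal figure is 2.5% on each side.

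- At 0.72 the linear lower limit lies above the true rate in 5.2% of trials (log(-log) 1.1%).
- At 0.796 it does so in 6.4% (log(-log) 0.8%); independent re-runs put the linear figure as high as 6.8%.
- At the 2-year 0.40 the tilt is the other way: the lower limit is too high in 2.7% and the upper limit too low in 3.8%. The flattering direction is therefore specific to the higher rates.

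**No loss (exact binomial), linear against log(-log).**

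- 0.40: 94.6% and 94.6%.
- 0.50: 91.9% and 94.0%.
- 0.72: 94.1% and 94.8%.
- 0.796: 92.3% and 97.0%.

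**Upper limit above 1.** Without loss this needs 37 to 39 of 40 event-free: at 37, 0.925 + 1.96 × 0.0416 = 1.007; at 36, 0.900 + 1.96 × 0.0474 = 0.993. The probability is 0.14% at 0.72 and 2.5% at 0.796 without loss. With 10% loss it is about 0.25% and 3.5%. In the 2-year cases it is at most 0.01% with 10% loss or less.

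**The case against.** The plan's formula is pre-specified, reproducible and referenced, and it describes precision in a 40-man phase 2 trial. Without loss, which is a case the section itself discusses, the two methods tie at 0.40 and differ by 0.8 points at 0.72 (unrounded coverages). That stands, and it limits how much weight the point deserves. The plan does budget for loss, however, and with loss the shortfall appears at every rate examined.

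A reader might also infer stronger claims that the documents do not support:

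- **Impossible limits are a real risk.** At a 1-year rate of 0.90 the upper limit would pass 1 in nearly half of trials, but no such rate appears in the plan. At the rates it uses or implies, the event is rare.
- **The trial's type I error is inflated.** Testing 50% with the linear 1-year interval has an exact two-sided error of 8.1% at n=40 without loss (6.5% at n=36). No such test is planned; the sample size rests on a one-sample log-rank test. The log(-log) interval also errs by 6.0% there, and at 0.618, the rate implied by the null median, the linear error is 5.0%.
- **The linear intervals are simply too narrow.** At rates of 0.40 to 0.50 they are wider than the log(-log) ones. The fault is mainly placement.
- **Log(-log) guarantees 95%.** Without loss it gives 94.0% at 0.50 and 97.0% at 0.796. It is closer to nominal on the whole, but not exact.
- **These intervals are the only inference described.** The same section also gives an interval for the median.

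**Conclusion.** The point holds as a minor one. With n=40 and 10% loss per year, the planned 1- and 2-year intervals cover about 92–94%, against about 95–95.7% for log(-log) intervals. At 1-year rates of 0.72 to 0.80 the lower limit is too high in about 5–7% of trials instead of 2.5%. The size rests on exponential event and loss times and on the assumed loss rate; with no loss the gain ranges from nothing at 0.40 to 0.8 points at 0.72. At 0.796 without loss, log(-log) overshoots to 97.0% while linear falls to 92.3%. Nothing here alters the log-rank test, the sample size or any stated decision rule.

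**What to change.** State in Section 10.1 that the 95% intervals for the 1- and 2-year PSA-PFS probabilities use the log(-log) transform of the Kaplan-Meier estimate with Greenwood's variance, and replace the linear formula. Name the transform explicitly instead of pointing to the software default: the documents do not say which transform that default applies.

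For consistency the same transform may be used when inverting for the median interval. That is optional, because no gain was shown there.

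The cost is one sentence and one software option, with no effect on patients, visits or sample size. The downside is asymmetric intervals, from about 3% narrower to 4% wider than the linear ones. If the margin-of-error calculation is kept, it should be labelled a linear-scale approximation used for planning.

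### The null median PSA-PFS of 1.44 years contradicts the null 1-year rate of 50%, so the single-arm benchmark is stated two incompatible ways

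*Combined protocol and SAP*

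**What the plan says.** The sample size justification in section 10.1 describes the hypotheses in one sentence: the median PSA-PFS times are "assumed to be 1.44 and 3.04 years (the corresponding 1 year PSA-PFS rates are 50% and 72% respectively". It then says that a one-sample log-rank test with n = 36 "has 82% power (two-sided test with significance level 0.05) to reject the null hypothesis if the median survival time is at least 3.04 years". The sample is raised to 40: "Taking into account of withdrawal or loss to follow-up (no more than 10% for the first year), we plan to recruit 40 patients".

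The next paragraph approximates the confidence interval margins, using 0.72 for 1-year PSA-PFS and 0.40 for 2-year PSA-PFS. The analysis text of the same section is about estimation: "Median PSA-PFS and 1-year and 2-year PSA-PFS probabilities will be estimated using the Kaplan-Meier method", with confidence intervals. It also plans to report "the number and percentage of subjects alive and without PSA progression at 1 and 2 years of follow-up". The one-sample log-rank test appears only in the sample size paragraph. Section 10.1 gives no survival distribution, accrual period, follow-up length or variance form for the power calculation.

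**The concern.** The median is the time at which PSA-PFS falls to 50%. A null rate of 50% at 1 year therefore puts the null median at 1 year, and a null median of 1.44 years cannot correspond to it. The two numbers for the alternative do not fit a constant hazard either.

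The trial has no control arm, so its fixed null is the only comparator. A reader may take that null to be 50% at 1 year (median 1.00 year) or a median of 1.44 years (62% at 1 year if exponential). A result between the two beats one benchmark and misses the other, and the choice could be made after the data are seen. It is also unclear which target the 82% power belongs to. The Kaplan-Meier estimates themselves are not affected.

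**Working it through.** **Inputs, all from section 10.1:** medians 1.44 and 3.04 years; 1-year rates 50% and 72%; n = 36; two-sided 0.05; power 82%; 10% loss; planning rates 0.72 at 1 year and 0.40 at 2 years.

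**Where 1.44 and 3.04 come from.** For an exponential with 1-year rate S(1), mean = -1/ln S(1) and median = ln 2/(-ln S(1)).
- 50%: mean = 1/0.6931 = 1.443; median = 1.00 year.
- 72%: mean = 1/0.3285 = 3.044; median = 0.6931/0.3285 = 2.11 years.

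Both printed medians match the means to two decimals.

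**The reverse reading.** With median m, S(1) = 0.5^(1/m).
- m = 1.44: S(1) = 0.618.
- m = 3.04: S(1) = 0.796.

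**Could another distribution reconcile the pairs?**
- Alternative: yes. A Weibull with S(1) = 0.72 and median 3.04 has shape 0.67.
- Null: no, unless the curve is exactly flat at 50% from year 1 to year 1.44, which the plan does not suggest.

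**The 2-year rate of 0.40.** A 3.04-year median requires S(2) of at least 0.50 under any distribution. Exponential 72% gives 0.72² = 0.52, and an exponential with median 3.04 gives 0.63. The Weibull of shape 0.67 gives 0.59. A Weibull through 0.72 and 0.40 has shape 1.48 and median 1.66 years, which is neither 3.04 nor 2.11.

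**Does the 82% identify the reading?** The hazard ratio is the same on both: ln 0.72/ln 0.50 = 0.474 and 1.44/3.04 = 0.474. What differs is how fast events accrue, so power depends on follow-up, which I have to assume. As a hand check, let O be the expected events under the alternative and E = O/0.474 the expected null cumulative hazard. With averaged variance, power is about Φ[(E - O)/√((E + O)/2) - 1.96].
- Rates, 1 year each: O = 36 × 0.28 = 10.08, E = 21.27. The ratio is 11.19/3.96 = 2.83, so power is Φ(0.87) = 81%.
- Medians, 1.5 years each: O = 10.43, E = 22.01. The ratio is 11.59/4.03 = 2.88, so power is Φ(0.92) = 82%.

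Simulated power (exponential, n = 36, 60,000 runs), for variance E / averaged (E + O)/2 / variance-stabilised:

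| Follow-up per patient | Rates 50%/72% | Medians 1.44/3.04 |
|---|---|---|
| 1 year | 73 / 81 / 81% | 56 / 69 / 70% |
| 1.5 years | not tabulated | 75 / 82 / 82% |
| 2 years | 92 / 95 / 95% | 85 / 89 / 89% |

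An exact binomial rule at 1 year (at least 24 of 36 progression-free) also gives 81.7% for 50% versus 72%. A formula using the exact variance under the alternative reaches 82% at 1.34 years for the rates and 1.93 years for the medians. So 82% can be reached on either reading, but not on the same schedule.

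**If the wrong null is carried into the test** (ranges over the three variance forms):

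| Follow-up | Null median 1.44, truth 72% at 1 year: power | Null 50% at 1 year, true median 1.44: success declared |
|---|---|---|
| 1 year | 18–29% | 25–34% |
| 2 years | 34–43% | 40–47% |
| 3 years | 44–51% | 48–54% |

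**Enrolment.** 36/0.90 = 40 reproduces.

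**The case against.** The best defence is that this is a slip with an obvious reading. Two printed values that equal exponential means to two decimals point to a mean labelled as a median. Other cues favour the rates: the margin line reuses 0.72 at 1 year, losses are counted over the first year, and about 82% is reached at 1 year of follow-up, the only horizon the sample size paragraph names. The site's retrospective series (sections 1.2 and 1.3) had a median PSA response of 10.5 months, nearer to 1.00 than to 1.44 years. That cue is weak: it covers 21 patients, measures response duration rather than PSA-PFS, and is not cited as the source of the null.

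Much of this stands, and I take 50%/72% as the likely intention. It does not remove the problem, because the power sentence repeats the 3.04-year median as the target and nothing elsewhere corrects it.

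Three further limits are fair:
- The wrong-null figures apply only if the wrong null is actually tested. Counting success at a true median of 1.44 years as false presumes that 1.44 is the null.
- The follow-up needed depends on the variance form, so neither 1 year nor 1.5 years is exact.
- The 0.40 enters only a margin of error, where it hardly matters: 1.96√(p(1 - p)/40) is 0.152 at 0.40, 0.155 at 0.52 and 0.149 at 0.63.

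**Conclusion.** The concern holds. The null is stated in two ways that cannot both be true, and the contradiction needs no exponential assumption. Under an exponential model the gap is a null median of 1.00 against 1.44 years, or a null 1-year rate of 50% against 62%; for the target it is 2.11 against 3.04 years, or 72% against 80%.

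The 82% power is not shown to be wrong. It cannot be tied to one target, because the follow-up and variance form it rests on are not stated. The hazard ratio, the inflation from 36 to 40 and the Kaplan-Meier estimates are unaffected. The power figures rest on exponential survival and on follow-up lengths that I assumed. This must be corrected, because the contradictory sentence is the only definition of the benchmark for the primary endpoint.

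**What to change.** State one coherent pair in section 10.1 and use it throughout.
- **Most likely intention:** 1-year PSA-PFS of 50% versus 72%, with exponential medians of 1.00 and 2.11 years.
- **Otherwise:** medians of 1.44 versus 3.04 years, with exponential 1-year rates of 62% and 80%.

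Reword the power sentence to that target, with the distribution, variance form, accrual and follow-up that produce the 82%. Name the one-sample log-rank test against that null in the analysis text, beside the Kaplan-Meier estimates. Bring the 2-year planning rate into line (exponential: 0.52 for 72% at 1 year, 0.63 for a 3.04-year median), or justify 0.40 with a named non-exponential curve.

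The cost is protocol wording and one recalculation. On the 50%/72% reading no extra patients are needed, provided the follow-up suits the variance form: about 1 year with averaged or stabilised variance, somewhat longer with variance E, which gives 73% at 1 year. On the 1.44/3.04 reading, 82% needs about 1.5 years per patient or more, and about 1.9 years by the exact-variance formula.
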